These adverse events do not occur randomly across the day (28) but are clustered around a morning vulnerable period (29-31). This daily pattern of vulnerability likely emerges from three sources. First, CV responses to rapid changes in behavior during the morning—including waking from sleep, posture changes, and sudden physical activity—precipitate adverse events (17,18,32-34). Second, the time of day itself represents a time of vulnerability to CV events due to the function of the circadian clock that times 24 h rhythms in physiology and behavior (Clock-Risk Model) (35,36). The likeliest scenario, is a mixture of these, in which a behavior like exercise is harmless at most times of day, but may trigger an adverse event in this clock-defined window of vulnerability (Clock-Reactivity Model). Thus, we aim to determine how obesity affects: (1) circadian rhythms of CV function and (2) the time-of-day dependent reactivity of the CV system to typical physical stressors i.e., posture and exercise.

Studying circadian rhythms in humans. To separate the endogenous circadian and behavioral influences on CV function in humans, our research team has applied ‘Forced Desynchrony’ protocols – as proposed in the current study. This separation is achieved by scheduling all behaviors evenly across all phases of the circadian cycle via numerous recurring days that have non-24 h periods while the participant remains in dim light to avoid circadian entrainment to light (37,38). Using this technique, we discovered in healthy lean individuals that certain CV risk factors surge around the vulnerable morning period for increased MI and CV deaths, including circulating cortisol (39), sympathetic activation, cardiac vagal withdrawal, heart rate (HR) (39), (40), platelet aggregability (41) and the pro-thrombotic plasminogen activator inhibitor-1 (PAI-1) (42). These circadian rhythms are presumably beneficial in healthy people as they prepare individuals for rapid physiological responses associated

[figure not shown]

Fig. 1. The FD consists of a baseline night and day, then ten 5 h 20 m cycles of sleep (black) and wake (gray). Stressors are scheduled each wake period. Lights are dim (≤ 3 lux). Letters indicate PET scanning for cardiac sympathetic function. Each participant undergoes up to 3 scans across the entire FD, 16 h apart across the circadian cycle, in a randomized order (a1, a2 & a3, or b1, b2 & b3, or c1, c2 & c3, balanced among participants).

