Acclimatization and baseline day: Participants report to the laboratory at Oregon Clinical & Translational Research Institute (OCTRI) on day 1 and are admitted to an individual room free of external time cues (e.g., clocks, radios, computers, visitors and sunlight). Participants maintain contact with study investigators. Room temperature is maintained at 21-22.2 °C and light intensity set at ≤ 3 lux during scheduled wakefulness and <0.2 lux (darkness) during scheduled sleep opportunities. Participants will be instrumented for full polysomnography, and a Holter monitor throughout the study. Our laboratory suites have a porthole for 24 h blood sampling without disturbing sleep and an IV line will be inserted and kept patent by a heparin solution.

Investigators/nurses are present in the lab or in a central control room 24h/day to monitor subject health, data acquisition, provide meals, collect biologic specimens, perform tests, and record sleep. A physician is always on call when a participant is in the laboratory. An extensive series of written protocols and checklists and team practices are used to ensure uniformity in execution of standard procedures.

FD Protocol (Fig. 1): Designed by Kleitman (37), the FD protocol desynchronizes the sleep-wake cycles from the circadian pacemaker and is performed in dim light to ensure the circadian pacemaker 'free-runs' at its intrinsic rate of ~ 24.1 h (43). At ~ 6 PM on day 2 after having been awake for 10 h, a participant's sleep-wake cycle is scheduled to a period of 5 h 20 min with a 2:1 ratio of wake: sleep-opportunity.

Imaging: PET imaging of the heart (detailed below in section 6h) will occur up to 3 times for each subject across the FD protocol (Fig. 1). The scans will be a minimum of 16 h apart (Fig. 1) and represent up to 3 different circadian phases.

Cardiac ultrasound: Myocardial perfusion imaging (detailed in section 6i) may occur up to 3 times for each

participant across the FD protocol.

5. Study Population

a. Number of Subjects

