performed, participants will be instrumented with EKG and an automated sphygmomanometer. Non-invasive BP recordings on a beat-by-beat basis (Nexfin, Netherlands) and may also be performed. The Nexfin finger cuffs will be placed on the non-dominant hand and held in place by an arm sling so that the BP cuffs will be at heart level. BP and HR will be assessed while participants stand up from a semi-recumbent posture and remain standing for ~5 min. A tilt table may also be used to transition the participant from supine to vertical posture at a controlled rate. For this procedure, participants will be strapped to a hydraulic tilt table with a weight-bearing footboard. Measurements will then be made under 3 conditions: (1) Baseline: Participants lie supine (0-degrees), awake and resting for approximately 20-min (2) 60 degree tilt: within a 3 to 5 sec period the table will be tilted to a 60-degree head-up angle. The table will be held here for a further 15-minutes (except in situations where the participant becomes uncomfortable, dizzy or faint). (3) Recovery: Within a 3 to 5 second period the table will be tilted to a 0-degree angle. The table will be held here for a further approximately 20-min.

- h. **Proton Emission Tomography (PET):** PET imaging of the heart will occur up to 3 times across the FD protocol (minimum 16 h between scans), with order randomized for each participant and beginning ~40 min after waking (**Fig.1**).

We will use O-15 water for blood flow, C-11 – meta-hydroxyephedrine for presynaptic norepinephrine transporter function and CGP 12177 for measure of beta adrenergic receptor density.

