- iii. **Specimen Handling:** Blood and urine samples will be identified only by the code assigned at the initial phone screen. Processing and handling of samples will be done by the OCTRI nursing and core lab staff. Samples will be stored and maintained by the OCTRI core lab -80 degree freezers. Access to study samples at OHSU will be limited to OCTRI core lab staff and study personnel listed on the IRB approved protocol. Coded biological samples may be sent to outside labs for analysis.

b. **Sharing of Results with Subjects**

With their consent, we will make known to the participant some of the information we have gathered from the physiological testing during screening and in the laboratory. There is a chance that the pre-study screening or the various blood and urine samples taken during the study will reveal some medical abnormality. This information will be conveyed to the participant, together with a recommendation to discuss the results with a physician if appropriate. Specifically, since genetic information obtained does not have medical or treatment importance at this time it will not be shared with the participant.

8. Data Analysis

Analysis of circadian rhythmicity: Forced desynchrony data is composed of circadian effects (intrinsic period ~24 h), evoked effects (5 h 20 min behavioral cycles) and 'noise'. The intrinsic period of the circadian pacemaker will be assessed with standard techniques as used for 20 years by the Principal Investigator (65,66). This intrinsic period, derived from melatonin, will be used to assign a circadian phase (from 0° to 360°) to each minute of the study, with 0° corresponding to the minimum of the waveform fitted to the DLMO data from the FD portion of the study. Analysis then proceeds in two ways. (A) Binning: Data for each variable and each participant will be 'binned' according to circadian phase and an average value per bin will be calculated. Data will then be averaged across participants. Bin size will be determined by the nature of the data being analyzed; in most cases we have found that a bin size of 60° (~4 h) allows sufficient detail while at the same time provides data for each participant in each bin. (B) Cosinor analysis to estimate rhythm amplitude and phase (67): Using regression techniques, time series data, not necessarily evenly spaced, can be fit to the function. This can be done within-subject, so standard deviations of amplitude and phase can be estimated (68).

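### PET allocation randomizes the scan set, not the order of circadian phases, and no stated analysis has a scan-number term to separate drift from rhythm

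*Combined protocol and SAP*

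**What the plan says.** The Fig. 1 legend (Section 3, Background) describes "then ten 5 h 20 m cycles of sleep (black) and wake (gray". It allows each person at most three PET scans with a 16 h gap, and says that they take place "in a randomized order (a1, a2 & a3, or b1, b2 & b3, or c1, c2 & c3, balanced among participants". Section 6h (PET) repeats the idea: "with order randomized for each participant and beginning ~40 min after waking". Section 4 (Imaging) words the spacing differently: "The scans will be a minimum of 16 h apart (Fig. 1) and represent up to 3 different circadian phases"; Section 6h also gives 16 h as a minimum. The forced desynchrony starts at the same point for everyone: "At ~ 6 PM on day 2 after having been awake for 10 h".

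Section 8 gives two general rhythm analyses for the trial: averaging within phase bins, and cosinor regression. Of the cosinor it says: "This can be done within-subject, so standard deviations of amplitude and phase can be estimated". Neither has a term for scan number or time in the study. The PET part of Section 8 covers image quantification only. A mixed model is named only for myocardial perfusion imaging, with circadian time as its one stated predictor. No text says whether sets are balanced within the lean and obese groups.

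**The concern.** Randomizing the order of three phases would normally spread time-in-study effects evenly over phase. Here the wording promises that protection, but the layout gives only part of it. A trend over successive scans (accumulating sleep loss, falling hematocrit, fluid loss, repeated tracer, habituation) would then be read partly as a circadian rhythm.

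Aim c asks how pre- and postsynaptic cardiac function vary across the circadian cycle in lean and obese participants. A spurious rhythm bears directly on the first half of that question. If the sets also fell unequally on the two groups, the same drift would differ between them and look like a group-by-phase difference.

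**Working it through.** **Inputs.** Ten cycles of 5 h 20 min, 16 h spacing and three sets (Fig. 1 legend); intrinsic period about 24.1 h (Section 4); 14 lean and 14 obese (Section 5a). Assumed: which cycles form sets a, b and c. The size of any drift, d per scan, is not given, so results are in units of d.

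**1. Schedule.** 3 × 5 h 20 min = 16 h 00 min, which reproduces the stated spacing. Phase step per scan = 360 × 16/24.1 = 239° (240° at 24.0 h); per cycle about 80°. The third scan falls six cycles after the first, so exact spacing allows only cycles 1-4-7, 2-5-8, 3-6-9 or 4-7-10. Relative phases for the first three are 0, 240, 120; 80, 320, 200; and 160, 40, 280 degrees. The opposite sequence (+120° per scan) needs steps of six cycles (6 × 80 = 480 = 360 + 120), that is cycles 1, 7 and 13; there are ten.

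**2. One participant.** Let the outcome be −d, 0, +d over scans 1 to 3 at phases 0°, 240°, 120°, with no rhythm.
- cos coefficient = (2/3)(−d × 1 + d × (−0.5)) = −d
- sin coefficient = (2/3)(d × 0.866) = 0.577d
- amplitude = √(1 + 0.333) d = 1.155d

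The fit is perfect (R² = 1): mean, cosine and sine use all three points, leaving no residual degrees of freedom. Pure noise gives a mean amplitude of √(2/3) × √(π/2) = 1.02 within-person SD. With fewer than three scans the model cannot be fitted at all.

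**3. Pooled over sets.** Starting a set at phase θ rotates the spurious vector by θ. The pooled amplitude is therefore 1.155d × ρ, with ρ = |Σ n·exp(iθ)| / Σ n over sets. R² of linear scan number on cosine and sine is ρ², and the largest variance inflation from adding scan number is 1/(1 − ρ²). At 240° steps:

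| Starting cycles | Split | ρ | R² | Spurious amplitude | Inflation |
|---|---|---|---|---|---|
| 1, 2, 3 (or 2, 3, 4) | equal | 0.449 | 0.20 | 0.52d | 1.25 |
| 1, 2, 3 | 10/9/9 | 0.441 | 0.19 | 0.51d | 1.24 |
| 1, 2, 3 | 5/5/4 | 0.474 | 0.22 | 0.55d | 1.29 |
| 1, 2, 4 (or 1, 3, 4) | equal | 0.228 | 0.05 | 0.26d | 1.05 |

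Example, equal split on cycles 1, 2, 3: ρ = (1 + 2 cos 80°)/3 = 1.347/3 = 0.449. With a 24.1 h period the four amplitudes are 0.51d, 0.51d, 0.54d and 0.26d.

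**4. Between groups.** With drift d common to both groups and sets on cycles 1, 2, 3, the spurious difference in rhythm vector is 1.155d times the distance between the two groups' weighted mean directions.
- Same split in both groups: 0.
- 5/5/4 against 5/4/5: 1.155d × (2 sin 40°)/14 = 0.11d.
- 7/4/3 against 3/5/6: 0.57d.

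If balance were only overall (10/9/9) and unrelated to group, the chance of x, y, z lean participants in the three sets is C(10,x)C(9,y)C(9,z)/C(28,14). Summing, some set differs between groups by 3 or more in about 63% of allocations and by 4 or more in about 32%; both groups get a 5/5/4 split in about 20%.

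**The case against.** The strongest reply has several parts.

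- **Allocation is stated as randomized and balanced.** A reader might infer that PET timing is not randomized at all. The documents do not support that. Participants are randomized to a set, and staggered starts are what make scan number and phase separable: pooled R² is about 0.20 or less, not 1. This stands, but the separation happens only if scan number is in the model.
- **Spacing may exceed 16 h.** Sections 4 and 6h say minimum, which admits 20 cycle triples, not all with +240° steps (1-6-9 gives 0, 40, 280). The fixed sequence is therefore a reading of the legend, which states 16 h and lists three sets. This limits certainty about the layout.
- **Group imbalance is not shown.** A reader might infer that sets are unbalanced within lean and obese. The plan neither states nor excludes within-group balance, and the 63% and 32% figures apply only if allocation ignores group. Imbalance alone also produces no group-by-phase bias under a single-harmonic rhythm; unmodelled drift is needed too. Mean lean-obese differences are unaffected in participants with all three scans, since every set covers scans 1 to 3 at phases 120° apart.
- **No drift is demonstrated.** Short-lived tracers, long gaps and a baseline day reduce some sources. However, Section 6p allows for possible sleep deprivation, and Section 11a expects a small hematocrit fall and possible fluid loss.
- **The within-subject cosinor is general text, not a commitment for PET.** True. But no other statistical model for PET is given, and binning has no scan-number term either.
- **PET is not among the six powered comparisons in Section 9.** True, though it is aim c and is listed under the primary dependent variables in Section 6o.

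**Conclusion.** The point holds in a limited form. On the legend's 16 h spacing, the set is randomized and the phase sequence is not. Scan number is completely confounded with phase within a participant and partly confounded across sets. Nothing in Section 8 adjusts for it.

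A drift of d per scan would appear as an amplitude of about 0.26d to 0.51d pooled, depending on which starting cycles are used, and about 1.15d in an individual three-point fit. A spurious group-by-phase difference needs both drift and unequal set distribution, and would be small if the splits are nearly alike. These results rest on exact 16 h spacing, three scans per participant, near-equal sets and an inferred set layout. Whether d is large enough to matter cannot be judged from the documents. The case for changing the plan is that protection is cheap, not that bias has been shown.

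**What to change.** 1. Describe the allocation as randomization to a set, list the cycle numbers of each set in the text, and reconcile the 16 h and minimum 16 h wordings.
2. Allocate sets in blocks within lean and within obese, 5/5/4 in each with the same split in both. A drift common to both groups then cancels from the group contrast, approximately so if some scans are missed.
3. Analyse each PET outcome in one mixed model: participant as random effect; group, cosine, sine, group × cosine, group × sine and scan number as fixed effects. Use this instead of individual cosinors. It also takes participants with fewer than three scans.

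Step 2 alone does not remove the phase-scan confounding (R² stays at about 0.22 with 5/5/4); the scan-number term in step 3 does. The cost is an allocation list, a paragraph of analysis text, one model degree of freedom for a linear scan term, and variance inflation of at most about 1.25 to 1.3 on the rhythm terms.

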Endogenous circadian rhythms of cardiovascular (CV) risk factors are rarely studied in obese humans. Thus, we aim to determine whether obese individuals have elevated morning CV risk because of normal CV rhythms on top of their existing increased CV risk (e.g., hypertension and increased sympathetic activation), or whether obesity disrupts CV rhythms and thereby furthers CV risk. Using an established multi-day circadian protocol in humans performed in dim light with behaviors scheduled evenly across the entire circadian cycle, our aims are to determine: (1) if obese individuals have normal or abnormal basal circadian CV rhythms, and (2) if obese individuals have normal or abnormal circadian rhythms in CV reactivity to stresses.

Specifically, we aim:

- a. To test if the circadian amplitudes and phases of important obesity-related CV risk markers are affected by obesity. We hypothesize that there will be endogenous circadian rhythms in CV risk markers including important hemodynamic variables (blood pressure, heart rate, vascular endothelial function), plus circulating markers of prothrombotic state, oxidative stress and inflammation in both obese and lean individuals. We expect the mean levels of these markers to be impaired in obese individuals along with changes in circadian rhythm amplitude contributing to increased CV risk during the morning period of CV vulnerability.
Sub aim a1: Determine in lean healthy humans if CMF, measured as coronary microvascular blood flux, has an endogenous circadian rhythm with lowest function in the morning.
i. Sub aim a2: Test the hypothesis that people with obesity have impaired coronary microvascular blood flux compared to lean individuals, with the exaggerated impairment during the morning.

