Obesity and cardiovascular risk. The prevalence of obesity in the US has increased dramatically over the last 25 years such that now over a third of adults are obese, and this is projected to reach 50% by 2030 (7-9). Obesity increases the risk for cardiovascular (CV) disease, the leading cause of death in both males and females (10-12). Increased body fat, in particular central adiposity, contributes substantially to circulating levels of leptin, tumor necrosis factor- α (TNF- α), interleukin-6 (IL-6) [leading to CRP release from the liver], plasminogen activator inhibitor-1 (PAI-1), and angiotensinogen leading to a relatively pro-thrombotic state with chronic inflammation, increased sympathetic nervous system (SNS) activation, hypertension (HTN) and obstructive sleep apnea (OSA) – all notable CV risk factors (13-18). There are also adaptations in cardiac structure and function with increased adiposity even in the absence of HTN or other pathological states (19,20). To meet increased metabolic needs with obesity, blood volume and cardiac output increase, leading to heart chamber enlargement, left ventricular hypertrophy, reduced diastolic compliance, increased left ventricular filling pressure and in some cases, heart failure. Obesity related systemic HTN combined with other cardiometabolic risk factors leads to coronary heart disease (19). Ultimately, there is a fivefold increased risk of death from CV disease in obese individuals (21,22).

Circadian pattern of adverse CV events. Overall, obesity increases the risk of adverse CV events including myocardial infarction (MI) (23,24), sudden cardiac death (SCD) (12,25,26), and stroke (27).

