Bristol Myers Squibb) will be used. One vial of Definity (1.3 mL) will be diluted to a total volume of 30 mL and infused at 1.5 ml/min intravenously. Myocardial contrast echocardiography will be performed with a phased-array transducer interfaced with an ultrasound system (iE33, Philips Ultrasound). A contrast-specific multipulse amplitude-modulation sequence will be performed at a centerline transmission frequency of 1.8 MHz, a mechanical index of 0.12, and a compression of 60. Images will be acquired in the apical 4-chamber, 2- chamber, and 3-chamber views. End-systolic images will be acquired for 10 seconds after a 5-frame destructive pulse sequence performed at a mechanical index of 1.0. Vasodilator stress will be applied using i.v. regadenoson and echocardiography will be repeated to measure the effect of hyperemia.

- j. **Exercise Test:** All team members have extensive experience in performing exercise testing under laboratory conditions. The power setting of the cycle ergometer will be tailored to induce 50% HR_{MAX} for each individual during their initial exercise test and kept constant for subsequent tests to enable us to quantify changes across the circadian cycle. This workload is similar to that in our preliminary data and chosen to reflect the type of workload placed on the CV system during normal daily activities (e.g. walking). This level elicits characteristic hemodynamic responses without causing an anaerobic state or training effects (48,49). The procedure is: (i) sit quietly on the ergometer for 5-10 min for baseline recordings; (ii) cycle for 15 min at 50% HRmax, and (iii) remain on the ergometer, stationary and resting for a 5-10 min recovery period.
- k. **Energy Expenditure:** We will measure energy expenditure via indirect calorimetry for assessment of EE and macronutrient oxidation (calculated using equations of (Jequier, 1987) during different portions of the inpatient protocol. O2 consumption and CO2 production are used to calculate metabolic rate and the oxidation of carbohydrate and fat (50).

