Analysis of myocardial perfusion imaging. Image analysis will be conducted offline. The immediate post-destruction frame will be digitally subtracted from all subsequent frames. Time versus background subtracted intensity will be measured on the background-subtracted frames from regions-of-interest placed over the myocardium according to the American Society of Echocardiography's 17-segment model. Data will be fit to the function $y=A(1-e^{-\beta t})$ where y is the video intensity at time t ; A is plateau video intensity, an index of capillary blood volume and β is the rate constant which provides a measure of average erythrocyte flux rate. Microvascular blood flow will be calculated by the product of A and β . Since flow reserve and β -reserve can be abnormal from increased resting values more so than reduced stress values, the definition of microvascular dysfunction will also require that complete refill of the microcirculation take >2 postdestructive beats. These data will be further analyzed using mixed model analysis with β -reserve as the primary dependent variable and circadian time as the independent variable.

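### Plateau intensity A is not scaled to the blood pool, so obese–lean comparisons of A and of A × β can come out lower in obesity from contrast dilution alone

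*Combined protocol and SAP*

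**What the plan says.** Section 6i (Perfusion imaging) describes the contrast infusion: "One vial of Definity (1.3 mL) will be diluted to a total volume of 30 mL and infused at 1.5 ml/min intravenously". It has no term for weight, blood volume or cardiac output. The same section records a compression setting of 60 and repeats the imaging after regadenoson.

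Section 8 (Analysis of myocardial perfusion imaging) uses "regions-of-interest placed over the myocardium according to the American Society of Echocardiography's 17-segment model" and names no cavity region. It describes one intensity correction: "The immediate post-destruction frame will be digitally subtracted from all subsequent frames". On the fitted curve it says "A is plateau video intensity, an index of capillary blood volume and β is the rate constant", and then "Microvascular blood flow will be calculated by the product of A and β". The only model it names is a mixed model with β-reserve as primary dependent variable and circadian time as independent variable. Flow reserve enters through the definition of microvascular dysfunction.

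On physiology, section 3 (Background) says that in obesity "blood volume and cardiac output increase, leading to heart chamber enlargement". Sub aim a2 hypothesises that "people with obesity have impaired coronary microvascular blood flux compared to lean individuals". Section 9 assigns 10 lean and 10 obese participants to sub aims a1 and a2.

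**The concern.** Plateau intensity reflects two things: how much capillary blood lies in the region, and how many microbubbles each unit of that blood carries. Subtracting the post-destruction frame removes background but does not correct for the second. By the protocol's own account, the second should differ between the groups: the infusion is the same for all, and the obese group is described as having larger blood volume and cardiac output. The groups are selected to differ in body size (BMI 30 to below 40 against above 18.5 to below 25 kg/m²), so contrast dilution is confounded with group.

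The resulting shift lowers A and A × β in obesity. A reader who takes *blood flux* in sub aim a2 to mean A × β could then count a measurement artefact as support for the hypothesis.

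**Working it through.** **Plan's own figures.** The documents give no expected value, SD or group difference for A, β or A × β. Section 9 claims 80% power for sub aims a1 and a2 without an effect size, SD or alpha, so there is nothing to reproduce for this measure.

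**Step 1: delivery.** (1.3 mL / 30 mL) × 1.5 mL/min = 0.065 mL of agent per minute, the same for every participant.

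**Step 2: model.** Let V be capillary volume and c the blood concentration of microbubbles. Assume intensity is proportional to concentration (k is a constant) and, at a fixed infusion rate, c is inversely proportional to cardiac output. Then:

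- observed A = k × c × V
- observed A × β = k × c × V × β
- β does not contain c
- β-reserve = β(stress) / β(rest) does not contain c
- observed flow reserve = [c(stress) / c(rest)] × true flow reserve

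**Step 3: size of the shift.** If cardiac output is higher in obesity by a factor f and the microvasculature is identical, observed A and A × β are multiplied by 1/f. The documents give no value for f, so a range is assumed. The last three columns show the chance of a significant lower-in-obese result when there is no microvascular difference. They assume a two-sample t-test, 10 per group, two-sided alpha 0.05, and a between-person SD of 20%, 30% or 40% of the lean mean. The nominal rate in that direction is 2.5%.

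| f (assumed) | 1/f | Fall in A and A × β | SD 20% | SD 30% | SD 40% |
|---|---|---|---|---|---|
| 1.1 | 0.909 | 9.1% | 15.9% | 9.4% | 7.0% |
| 1.2 | 0.833 | 16.7% | 42.2% | 21.7% | 14.1% |
| 1.3 | 0.769 | 23.1% | 68.5% | 37.0% | 23.0% |

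For example, with f = 1.2 and SD 20%, the standardised shift is 0.167 / 0.20 = 0.83 SD, and the test rejects 42.2% of the time.

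**Step 4: check on the fitted curve.** The section 8 function was fitted to noise-free data with illustrative values: rest A = 10 and β = 0.40; stress A = 11 and β = 1.20; cavity intensity 100. Concentration was then lowered by a factor of 1.2 throughout, at rest and stress alike.

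| Quantity | Reference | Diluted |
|---|---|---|
| A, rest | 10.0 | 8.33 |
| A × β, rest | 4.00 | 3.33 |
| β, rest | 0.40 | 0.40 |
| β-reserve | 3.0 | 3.0 |
| Flow reserve | 3.3 | 3.3 |
| A / A_LV, rest | 0.100 | 0.100 |

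Dilution moves A and A × β by −16.7% and leaves the rate constant and both reserve ratios unchanged. Dividing by the cavity intensity removes the shift.

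**The case against.** The strongest reply is that the declared endpoint is untouched. β-reserve is the primary variable and does not contain A. Section 8 sets out no obese–lean test of A or of A × β, so the rejection rates above belong to an analysis the plan does not specify. This stands, and it limits the point to secondary measures.

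A reader might infer that the test of sub aim a2 is itself biased. The documents do not support that. Section 8 uses *flux* for β and *flow* for A × β, so a2 maps at least as naturally to β. Equally, the plan does not say which measure carries the obese–lean comparison, and its one model has no group term. The ambiguity is a reason to state the measure.

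A reader might also infer that flow reserve has the same problem. It does not: a constant per-person factor cancels in stress/rest. If regadenoson changes cardiac output, flow reserve shifts in both groups. A group bias arises only if the proportional change in concentration differs between obese and lean participants, and nothing in the documents indicates that.

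The size is open to challenge as well. The rise in cardiac output is assumed. So is linearity, and section 6i acquires with compression while section 8 mentions no linearisation. If intensity is compressed, 9–23% is not the expected fall, although A would still depend on concentration. Chest-wall attenuation may also matter but cannot be sized from the documents and is not counted here.

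Finally, [¹⁵O]-water PET (sections 6h and 6o) measures coronary flow without microbubbles. It is optional, so it mitigates only in part.

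**Conclusion.** The concern holds for obese–lean comparisons of A and of A × β at rest or under stress. As written, these secondary measures can be lower in obese participants with no microvascular difference. The shortfall is about 9%, 17% or 23% if cardiac output is 10%, 20% or 30% higher and intensity is linear in concentration. Both conditions are assumptions, so the range illustrates the size and does not estimate it.

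The concern does not reach β or β-reserve, and it reaches flow reserve only under a group difference that the documents do not indicate. Within-person circadian contrasts (sub aim a1) are much less exposed, because body size is constant within a person.

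**What to change.** Change section 8 (Analysis of myocardial perfusion imaging):

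1. Convert video intensity to a linear scale before any ratio is taken, and say how.
2. Divide each segment's A by the background-subtracted intensity of the adjacent left-ventricular cavity in the same view and at the same depth. Report flow as (A/A_LV) × β.
3. Flag views with a saturated or shadowed cavity and report their number by group. If they are more common in one group, exclusions could matter with only 10 per group.
4. State that the obese–lean test of *blood flux* in sub aim a2 rests on β and β-reserve, and that no between-group inference will be based on unnormalised A or A × β.

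β-reserve stays primary and the infusion does not change. The cost is one extra region of interest per view on images already planned, a linearisation step that may need raw data, some views that cannot be normalised, and a few lines of text. Item 4 alone needs no image work and already prevents the misreading.
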